10.3 ST. GEORGE’S RESPIRATORY QUESTIONNAIRE (SGRQ)

What is the St George’s Respiratory Questionnaire?

The SGRQ is designed to measure health impairment in patients with asthma and COPD. It is also valid for use in bronchiectasis and has been used successfully in patients with kyphoscoliosis and sarcoidosis. It is not suitable for cystic fibrosis. It is in two parts. Part 1 produces the Symptoms score, and Part 2 the Activity and Impacts scores. A Total score is also produced.

Part 1 (Questions 1 to 8) covers the patients’ recollection of their symptoms over a preceding period that may range 1 month to 1 year. It is not designed to be an accurate epidemiological tool; its purpose is to assess the patient’s perception of their recent respiratory problems. The original version was validated using a 12-month recall period. More recently a 1 month recall version (appropriately worded) has been validated. This has slightly weaker psychometric properties than the 12-month version and produces a marginally lower Symptom score and Total score. A 3-month recall period has been used very satisfactorily. In summary, the 3-month and 1-year versions provide the best properties, with no specific advantages to either. The 1-month version should only be used when the time frame of the study dictates.

Part 2 (Questions 9 to 16) addresses the patients' current state (i.e. how they are these days). The Activity score just measures disturbances to patient's daily physical activity. The Impacts score covers a wide range of disturbances of psycho-social function. Validation studies showed that this component relates in part to respiratory symptoms, but it also correlates quite strongly with exercise performance (6-minute walking test), breathlessness in daily life (MRC breathlessness score) and disturbances of mood (anxiety and depression). The Impacts score is, therefore, the broadest component of the questionnaires, covering the whole range of disturbances that respiratory patients experience in their lives.

How should it be administered?

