The questionnaire should be completed in a quiet area free from distraction and the patient should ideally be sitting at a desk or table. Explain to the patient why they are completing the questionnaire, and how important it is for us to understand how they feel about their illness and the effect it has on their daily life. Ask the patient to complete the questionnaire as honestly as possible and stress that there are no right or wrong answers; simply the answer that the patient feels applies to them. Explain that they must answer every question and that someone will be close at hand to answer any queries.

The SGRQ is designed as a supervised self-administered questionnaire. This means that the patients should complete the questionnaire themselves but someone should be available to give advice if it is required. The patient's responses should not be influenced by the opinions of family, friends or members of staff. The questionnaire is designed to elicit the patient's opinion of his/her health, not someone else's opinion of it. If the spouse or partner has accompanied the patient they should be asked to wait in a separate area. Similarly, do not allow patients to take the SGRQ home to be completed since you cannot be sure that it will be completed without the help of family or friends.

It is very important, once the patient has finished, that you check the questionnaire to make sure a response has been given to every question and return it the patient for completion of missed items, before the patient leaves.

What should I do about queries regarding completion of the questionnaire?

If a patient asks for help with a question, do not provide an answer for them. The point of the questionnaire is to get an understanding of how the patient views his or her illness. It is appropriate to clarify a question but not to provide an answer. Questions may be read aloud if patients have difficulty with reading, but the responses must be theirs alone. If a patient gives an answer you disagree with it is not appropriate to challenge their response or to query it. It is their view of their condition we are interested in – no matter how strange the response!

The following are notes which may help you explain to patients what is required

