1. In [Part 1](#) of the questionnaire, emphasise to patients that you are interested in how much chest trouble they have had over the last year. The exact period is not important. We are looking for an impression or perception of health.
2. Asthma and COPD can vary day-to day. In [Part 2](#), we want to know about the patient's current state (these days).
3. A severe or very unpleasant attack of chest trouble (Part 1, [Question 5](#)) is any attack that could be described that way in the patient's own judgement. Not 'severe' as defined by medical staff.

4. For Question 7 emphasise that you are interested in the number of good days that they have had.
5. Question 10 regarding employment can cause patients some problems. We are interested in how a patient's chest trouble affects their current working life or how it affected life when they were working. For example, if a patient took early retirement because of their chest condition, the response would be 10a – 'My chest trouble made me stop work', if a patient's retirement was unrelated to their chest trouble, their response would be 10c 'My chest trouble does not affect my work'.
6. Questions 11 to 16 require a response to every question. It may be worth emphasising this to the patient.
7. Many patients do not engage in physical activity. It is important to determine whether this is because they do not wish to (in which case the answer would be 'False') or cannot engage in these activities because of their chest trouble (in which case the answer would be 'True').
8. Medication questions refer to medications and treatments given for a patient's chest disease and may interfere with their life if, for example, they are on oxygen support and have to carry it around with them.
9. It should be emphasised that responses to Question 15 are in terms of breathing difficulties and not any other problems. If patients do not engage in activities described in certain items, they should tick 'False'. Patients who do not engage in these activities because they are limited by their breathlessness, should tick 'True'.

EXAMPLE OF QUESTIONNAIRE

ST. GEORGE'S RESPIRATORY QUESTIONNAIRE (SGRQ) ENGLISH FOR THE U.S.A.

This questionnaire is designed to help us learn much more about how your breathing is troubling you and how it affects your life. We are using it to find out which aspects of your illness cause you the most problems, rather than what the doctors and nurses think your problems are.

[figure not shown]

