*Please read the instructions carefully and ask if you do not understand anything.
Do not spend too long deciding about your answers.*

Before completing the rest of the questionnaire:

Please check one box to show how you describe your current health:

Very good	Good	Fair	Poor	Very poor
				

Copyright reserved

Tel.
Fax

St. George's Respiratory Questionnaire
PART 1

Please describe how often your respiratory problems have affected you over the past 4 weeks.

Please check (✓) one box for each question:

	almost every day	several days a week	a few days a month	only with respiratory infections	not at all
1. Over the past 4 weeks, I have coughed:					
2. Over the past 4 weeks, I have brought up phlegm (sputum):					
3. Over the past 4 weeks, I have had shortness of breath:					
4. Over the past 4 weeks, I have had wheezing attacks:					
5. How many times during the past 4 weeks have you suffered from severe or very unpleasant respiratory attacks?	Please check (✓) one: more than 3 times  3 times  2 times  1 time  none of the time 				
6. How long did the worst respiratory attack last? (Go to Question 7 if you did not have a severe attack)	Please check (✓) one: a week or more  3 or more days  1 or 2 days  less than a day 				
7. Over the past 4 weeks, in a typical week, how many good days (with few respiratory problems) have you had?	Please check (✓) one: No good days  1 or 2 good days  3 or 4 good days  nearly every day was good  every day was good 				

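### Appendix 10.3 gives two conflicting recall periods for SGRQ Part 1, one year in the staff note and four weeks on the form, so the window behind the Symptoms score is not fixed

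*Protocol*

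**What the plan says.** Change from baseline in the SGRQ at 12 and 24 weeks is a secondary endpoint (protocol Section 2.1.3; SAP Section 5.2.2). The questionnaire is completed at Visits 1, 2, 5 and 7 (protocol Section 5.1.2.2). Appendix 10.3 holds the background, the staff notes and the form.

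- **Scores.** "Part 1 produces the Symptoms score, and Part 2 the Activity and Impacts scores. A Total score is also produced".
- **Staff note 1, on Part 1.** Staff are to "emphasise to patients that you are interested in how much chest trouble they have had over the last year". It continues: "The exact period is not important. We are looking for an impression or perception of health".
- **Status of the notes.** They are introduced with "The following are notes which may help you explain to patients what is required".
- **The form, Part 1 header.** "Please describe how often your respiratory problems have affected you over the past 4 weeks".
- **The form, items.** Questions 1 to 5 and 7 each repeat the four-week period; Question 1 begins "Over the past 4 weeks, I have coughed". Questions 6 and 8 print no period of their own.
- **Background on versions.** Recall may run from one month to one year, and "The 1-month version should only be used when the time frame of the study dictates".

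Neither document says whether the note or the form governs. Part 2 asks about the patient's current state and carries no such conflict.

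**The concern.** Part 1 is the only source of the Symptoms score and contributes to the Total. A patient told to think about a year and a patient reading four weeks on the page are answering different questions. With about 54 sites (protocol Section 3.3) and no governing rule, practice could vary by site, by patient, or between visits for the same patient.

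Two things follow. First, a one-year window at week 12 or 24 reaches back well before the intervention began, which would tend to pull the arms together on Symptoms. Second, the appendix's own background says the one-month version yields slightly lower Symptoms and Total scores than the twelve-month one. If a patient's effective recall period changes between baseline and a later visit, part of the measured change would reflect recall length rather than health.

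Quality of life is one of the trial's main objectives (protocol Section 2.1.1), and even a descriptive result needs a defined recall period to be read properly.

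**Working it through.** The plan gives no figure to reproduce here. The check is a comparison of texts followed by simple arithmetic.

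**Which form is in use.** SAP Section 6.6.2.1 refers to protocol Section 10.3 for the questionnaire and treats answer 5 to Question 5 as meaning no attacks. That is the fifth option on the printed four-week form, so scoring is written for that form. The notes fit it less well: note 5 cites a numbered Question 10 with lettered options, while Part 2 of the printed form has unnumbered items and different wording. Global Amendment 1 records that the SGRQ was updated to its current version. It is a reasonable inference that the notes were carried over from an older form, but the documents do not say so.

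**Share of the recall window before baseline.** Let L be the recall length in days and t the days since Visit 2. The share is max(0, L − t)/L.

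Inputs: L = 28 (form) or 365 (note 1). The flow chart puts Visits 5 and 7 on days 85 and 169, so t = 85 − 1 = 84 and t = 169 − 1 = 168. Protocol Section 6.2.2 allows up to 6 weeks (42 days) of extra delay before rehabilitation starts, with later visits moving accordingly.

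| Assessment | t | Form, L = 28 | Note, L = 365 |
|---|---|---|---|
| Week 12 | 84 | 0% | 281/365 = 77.0% |
| Week 24 | 168 | 0% | 197/365 = 54.0% |
| Week 12, start delayed 6 weeks | 126 | 0% | 239/365 = 65.5% |
| Week 24, start delayed 6 weeks | 210 | 0% | 155/365 = 42.5% |

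The ±3-day window at Visit 5 moves the one-year share only between 278/365 = 76.2% and 284/365 = 77.8%. The delayed-start rows count time before Visit 2. Measured from the first rehabilitation day the shares stay at 77.0% and 54.0%, because the visits shift with that day. The 0% for the form holds for any assessment on day 29 or later.

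**What this implies for a treatment effect.** The shares above are shares of time, not of effect. To turn them into dilution one must assume how patients weight the period. If every day of a 365-day window counted equally and the effect were steady from day 1, the retained fraction would be 84/365 = 23% at week 12 and 168/365 = 46% at week 24. If recent weeks count for more, more is retained; if the effect builds up gradually, less is. The documents support no particular weighting, so these two figures are illustrations and not bounds.

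**The case against.** The strongest reply is that the printed form will usually prevail. "The SGRQ is designed as a supervised self-administered questionnaire": patients complete it themselves and staff advise only if needed. Four weeks stands in the Part 1 header and in six of its eight questions. The notes are offered as an aid, and note 1 itself plays down the exact period. The background describes Part 1 as capturing the patient's perception of recent problems, not an exact count over a fixed window. The same note applies in both arms and at baseline, so no mechanism for bias between arms is evident; what remains is possible dilution and noise. The SAP (Sections 4 and 7.5.2) now limits secondary endpoints to descriptive statistics after termination of the trial, so no SGRQ test is left to lose power.

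Most of this stands, and it limits the size of the point. A reader might infer that the week-12 Symptoms score will mostly describe the time before baseline, or that its effect shrinks to at most 23%. The first requires the spoken note to override the printed page, which the documents do not establish. The second requires equal weighting of all 365 days, which they do not support.

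Nor is the restriction on the one-month version a further contradiction, since assessments at 12 weeks may well be a time frame that calls for it.

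The conflict itself does not go away. The note says to emphasise the longer period, the appendix lets staff clarify questions and read them aloud, and so the instruction has a route to the patient. Calling the exact period unimportant does not settle which period applies when the items print a fixed one.

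**Conclusion.** The point holds as a document inconsistency: wrong as written, modest severity. Appendix 10.3 leaves the recall period for SGRQ Part 1 undefined between four weeks and one year. The share of the window before baseline could lie anywhere from 0% to about 77% at week 12 and from 0% to about 54% at week 24, depending on which instruction patients followed. The upper ends assume a literal 365-day recall and on-schedule visits.

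Any one-year recall would tend to dilute a rehabilitation effect on Symptoms and, in part, on the Total. The direction is reasonably clear; the amount cannot be derived from the documents. Activity, Impacts and the 6MWD are untouched, and with only descriptive analyses remaining, the consequence is for interpretation and not for any formal conclusion.

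**What to change.** In Appendix 10.3, change note 1 so that it uses the form's own four-week period, and delete the remark that the exact period does not matter. If any visits remain, tell sites of the correction. The cost is one sentence in the appendix and a short letter, with no added procedures.

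If data collection is complete, state in the report that the site note conflicted with the printed form, and show the Symptoms component separately from the Total in the descriptive SGRQ results. That costs a sentence and a few table rows. Affected visits cannot be flagged or set aside, because neither document provides for recording what staff told patients, so the caveat has to apply to the Part 1 data as a whole.

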10.4 ELECTRONIC DIARY WITH DAILY PROACTIVE TOOL

10.4.1 The PROactive Tool

The PROactive instrument for the daily assessment of physical activity (D-PPAC) will be used in the study. The D-PPAC exists in an electronic version.

The D-PPAC is a 'hybrid' instrument, combining a short list of PRO items and two activity monitor variables to assess physical activity experience, and provides a simple, valid and reliable measure of physical activity experience by COPD patients [R16-5353] which can also be used for other respiratory diseases.

The D-PPAC includes in total 9 items, measuring a physical activity 'Total Score' with 2 domains ('amount' and 'difficulty') (Figure 10.4.1: 1). The 'amount' domain is covered by 2 items (amount of walking outside and chores outside) and by 2 activity monitor outputs (vector magnitude units per minute (VMU/min) and steps/day). The 'difficulty' domain is covered by 5 items.

The instruments require both activity monitor data and item data on a daily basis. Adequate physical activity data are considered for days where more than eight hours of wearing time (during the day, from getting up in the morning, until going to bed in the evening) is available. It is possible that days with activity monitoring are missing or patients forget to fill in the daily PRO in the evening.

In order to obtain the D-PPAC scores (total, amount and difficulty), daily measurements from both activity monitor and questionnaire are merged, and daily scores are calculated.

The D-PPAC instrument is scored in a three steps process:

- First, domains are scored by simple adding items, which gives a value for 'amount' between 0 and 17, with higher values representing a high amount of activity, and a 'difficulty' score from 0 to 20 with a high value representing a lesser degree of difficulty. For the D-PPAC assessment the values are 0-17 for 'amount' and 0-20 for 'difficulty'. (Figure 10.4.1: 1) The step counts and VMU's need to be converted into the appropriate daily score category.
- In the second step, the raw scores are scaled to a score ranging from 0 to 100, based on results of Rasch analyses
- Finally the 'total score' is obtained calculating the average between two domains. This score has the same scale of two domains, from 0 to 100.

After calculating the daily scores, weekly averages can be calculated.

[figure not shown]

Figure 10.4.1: 1 D-PPAC items

10.4.2 Electronic Diary – PROactive Questionnaire

INSTRUCTIONS TO PATIENTS DAY 1:

Patients with chronic lung disease like you often report that they have problems during physical activity. By physical activity, we mean all activities that require movement of your body. Examples are household activities, walking, going to work, or getting dressed. However, please consider all activities you do, and not only these examples. We would like to know how you experienced your physical activity since you woke up TODAY.

Please complete this questionnaire in the evening before going to bed. Please select the box next to the response that best applies to you TODAY.

There are no wrong answers. We very much value your response.

INSTRUCTIONS FOR SUBSEQUENT DAYS:

We would like to know how you experienced your physical activity since you woke up TODAY. Please complete this questionnaire in the evening before going to bed. Please select the box next to the response that best applies to you TODAY.

	Difficulty score	Amount score
How much walking did you do outside today?  None at all  A little bit (up to 10 minutes in total)  Some (up to 30 minutes in total)  A lot (up to 1 hour in total)  A great deal (more than 1 hour in total)		0 1 2 3 4
How many chores did you do outside the house today? Some examples are gardening, taking the rubbish out, or doing small errands.  None at all  A few  Some  A lot  A large amount		0 1 2 3 4
How much difficulty did you have getting dressed today?  None at all  A little bit  Some  A lot  A great deal	4 3 2 1 0	
How often did you avoid doing activities because of your lung problems today?  Not at all  Rarely  Sometimes  Frequently  All the time	4 3 2 1 0	
How breathless were you in general during your activities today?  Not at all  A little bit  Moderately  Very  Extremely	4 3 2 1 0	
How tired were you in general during your activities today?  Not at all	4	

	A little bit	3	
	Moderately	2	
	Very	1	
	Extremely	0	
How often did you have to take breaks during your physical activities today?			
	Not at all	4	
	Rarely	3	
	Sometimes	2	
	Frequently	1	
	All the time	0	
PROactive daily steps score		Total steps per day	
	0		0
	1		1
	2		2
	3		3
	4		4
PROactive daily VMU score		Dynaport	
	0		0
	1		1
	2		2
	3		3
	4		4
	5		5
Total scores (sum above):		difficulty	amount

Figure 10.4.2: 1 Daily PROactive (D-PPAC) e-PRO

ITEMS FOR DAILY ASSESSMENT – Activity monitoring

Steps (total daily value)

- 0 to 1900 steps/day
- 1901 to 3700 steps/day
- 3701 to 5500 steps/day
- 5501 to 7300 steps/day
- >7301 steps/day

VMU (daily VMU/min)

- 0 to 50 VMU/min
- 51 to 110 VMU/min
- 111 to 190 VMU/min
- 191 to 270 VMU/min
- 271 to 440 VMU/min
- >441 VMU/min

10.5 KBILD

1

King's Brief ILD Questionnaire
(K-BILD)

This questionnaire is designed to assess the impact of your lung disease on various aspects of your life. Read each question carefully and answer by **CIRCLING** the response that best applies to you. Please answer **ALL** questions, as honestly as you can.

PATIENT INFORMATION:

Name:

Date:

1. In the last 2 weeks, I have been short of breath climbing stairs or walking up an incline or hill.

1. Every time
2. Most times
3. Several Times
4. Sometimes
5. Occasionally
6. Rarely
7. Never

2. In the last 2 weeks, because of my lung condition, my chest has felt tight.

1. All of the time
2. Most of the time
3. A lot of the time
4. Some of the time
5. A little of the time
6. Hardly any of the time
7. None of the time

3. In the last 2 weeks have you worried about the seriousness of your lung symptoms?

1. All of the time
2. Most of the time
3. A lot of the time
4. Some of the time
5. A little of the time
6. Hardly any of the time
7. None of the time

4. In the last 2 weeks have you avoided doing things that make you short of breath?

1. All of the time
2. Most of the time
3. A lot of the time
4. Some of the time
5. A little of the time
6. Hardly any of the time
7. None of the time

5. In the last 2 weeks have you felt in control of your lung condition?

1. None of the time
2. Hardly any of the time
3. A little of the time
4. Some of the time
5. A lot of the time
6. Most of the time
7. All of the time

6. In the last 2 weeks, have your lung symptoms made you feel annoyed or down?

1. All of the time
2. Most of the time
3. A lot of the time
4. Some of the time
5. A little of the time
6. Hardly any of the time
7. None of the time

7. In the last 2 weeks, I have felt the urge to inhale deeply and frequently known as "air hunger."

1. All of the time
2. Most of the time
3. A lot of the time
4. Some of the time
5. A little of the time
6. Hardly any of the time
7. None of the time

8. In the last 2 weeks, my lung condition has made me feel anxious.

1. All of the time
2. Most of the time
3. A lot of the time
4. Some of the time
5. A little of the time
6. Hardly any of the time
7. None of the time

9. In the last 2 weeks, how often have you experienced "wheezing" or whistling sounds from your chest?

1. All of the time
2. Most of the time
3. A lot of the time
4. Some of the time
5. A little of the time
6. Hardly any of the time
7. None of the time

10. In the last two weeks how much of the time have you felt your lung disease is getting worse?

1. All of the time
2. Most of the time
3. A lot of the time
4. Some of the time
5. A little of the time
6. Hardly any of the time
7. None of the time

11. In the last 2 weeks has your lung condition interfered with your job or other daily tasks?

1. All of the time
2. Most of the time
3. A lot of the time
4. Some of the time
5. A little of the time
6. Hardly any of the time
7. None of the time

12. In the last 2 weeks have you expected your lung symptoms to get worse?

1. All of the time
2. Most of the time
3. A lot of the time
4. Some of the time
5. A little of the time
6. Hardly any of the time
7. None of the time

13. In the last 2 weeks, how much has your lung condition limited you carrying things, for example, groceries?

1. All of the time
2. Most of the time
3. A lot of the time
4. Some of the time
5. A little of the time
6. Hardly any of the time
7. None of the time

14. In the last 2 weeks, has your lung condition made you think more about the end of your life?

1. All of the time
2. Most of the time
3. A lot of the time
4. Some of the time
5. A little of the time
6. Hardly any of the time
7. None of the time

15. Are you financially worse off because of your lung condition?

1. A significant amount
2. A large amount
3. A considerable amount
4. A reasonable amount
5. A small amount
6. Hardly at all
7. Not at all

Thank you for completing this questionnaire.

